10.2.4. Handling of hypersensitivity**1) Anaphylaxis**

Anaphylaxis is a rapidly progressing systemic severe allergy reaction that is a life-threatening acute immune response.

If symptoms suggesting anaphylactic shock (exacerbation of respiratory symptoms, oligopnea or peripheral organ dysfunction due to hypotension, allergic symptoms of skin-mucosal tissues, etc.) are detected within a few minutes of the administration of the IP, the IP administration should be stopped immediately, and the subject should be rested in supine position and with leg elevation, and avoid the issues caused by dyspnea or vomiting.

The IP administration must be stopped immediately.

If anaphylactic symptoms are evident, epinephrine IM (intramuscular) injection should be given to the median anterolateral side of the thigh. And the laboratory test required to diagnose to anaphylaxis like Tryptase etc. can be conducted according to the judgement of the investigator.

If necessary, treatment for dyspnea such as oxygen supply etc. and treatment for hypotension/shock such as intravenous infusion of fluid can be performed, and BP, pulse rate, respiration, and oxygen saturation can be monitored.

10.3. Endpoints**10.3.1. Primary endpoints**

To assess safety and tolerability of HM15136 after repeated subcutaneous (SC) doses for 12 weeks.

- Incidence of adverse events (AEs):
cardiovascular (CV) events, rash/inflammatory dermatitis and other skin disorders, gastrointestinal (GI) events, and gallstone formation (cholelithiasis) will be managed following separate AE guidance document of HM15136 [Appendix].
- Incidence of clinical lab abnormalities:
including serum amylase, serum lipase, coagulation, thyroid stimulating hormone (TSH), serum calcitonin. Only for female, LH (Luteinizing hormone) and FSH (follicle stimulating hormone) are additionally included.
- Immunogenicity:
Anti-drug antibodies (ADAbs), neutralizing antibodies (nAbs), anti-polyethylene glycol antibodies (anti-PEG)
- Incidence and severity of clinical findings on physical examination
- Change from baseline in vital signs:
Supine position blood pressure (BP), heart rate (HR), respiratory rate, and tympanic temperature
- Changes of blood pressure (BP) and heart rate:
BP assessed by 24-hour ambulatory blood pressure monitoring (ABPM);
HR assessed by 24-hour ambulatory electrocardiography monitoring (Holter ECG; central reader)
- Change from baseline in 12-lead ECG parameters:
the primary ECG endpoint will be QTcF
- Injection site reactions

To assess the pharmacokinetic (PK) profile of HM15136 after administration of repeated subcutaneous (SC) doses in obese subjects by, but not limited to:

- C_{max} : Maximum concentration
- T_{max} : Time to reach C_{max}
- C_{trough} : Trough serum concentration
- AUC: Area under the concentration-time curve

Ex.) AUC_{0-t} : AUC at steady state during the period of injection (AUC_{0-t} at steady state)

- K_{el} : Terminal elimination rate constant
- $t_{1/2}$: Terminal half-life
- CL/F: Apparent clearance
- V_z/F : Apparent volume of distribution

10.3.2. Exploratory endpoints

To assess pharmacodynamics (PD) properties of HM15136 after repeated SC doses

- Incretins / metabolic hormones
 - 1) Glucagon-like peptide-1 (GLP-1)
 - 2) Gastric inhibitory polypeptide (GIP)
 - 3) Glucagon
 - 4) Fibroblast growth factor 21 (FGF 21)
 - 5) Leptin
- Serum lipid profiles
 - 1) Total cholesterol
 - 2) Low-density lipoprotein (LDL)
 - 3) High-density lipoprotein (HDL)
 - 4) Very low-density lipoprotein (VLDL)
 - 5) Triglycerides
 - 6) Free fatty acids (FFAs)
- Amino-acid profile
- Glucose metabolism parameter
 - 1) Fasting plasma glucose (FPG)
 - 2) Fasting insulin, Fasting C-peptide
 - 3) 7-point Self-monitoring of blood glucose (SMBG)
 - 4) HbA1c
 - 5) Fructosamine
 - 6) Glycated albumin
- Insulin resistance
 - Homeostatic Model Assessment for Insulin Resistance (HOMA-IR)
- Insulin secretion function
 - Homeostatic Model Assessment for β Cell Function (HOMA- β)
- Assessment of absolute and % changes of liver fat via MRI-PDFF (Magnetic resonance imaging-estimated proton density fat fraction)
(However, assessment of liver fat via MRI-PDFF will only be performed on day 85, if the liver fat prior to the first dosing $\geq 10\%$)
- Changes in visceral fat volume, determined by absolute and relative percent change assessed by MRI

- Body weight
- Body mass index (BMI)
- Waist circumference
- Hip circumference
- Waist-to-hip ratio (WHR)
- Temperature (tympanic)
- Inflammatory markers
 - 1) High-sensitive C-reactive protein (hs-CRP)
 - 2) Adiponectin
- Keton body
 - β -hydroxybutyrate

10.4. Safety assessment

10.4.1. Adverse Event (AE)

Reporting of AEs will begin from the date each subject signs an informed consent form (ICF) and will continue until the follow-up visit.

10.4.2. Definition of AE

An 'Adverse Event (AE)' is any untoward medical occurrence and unintentional sign, symptom or disease in a clinical study, and which does not necessarily have a causality with the IP. Concomitant conditions that existed prior to signing the ICF are not considered adverse events unless they worsen during the study. The pre-existing conditions are recorded as part of the subject's medical history.

An 'Adverse Reaction' is defined as any adverse event caused by a drug. Adverse reactions are a subset of all suspected adverse reactions where there is reason to conclude that the drug caused the event.

A 'Suspected adverse reaction' is defined as any adverse event for which there is a reasonable possibility that the drug caused the adverse event. For the purposes of IND safety reporting, 'reasonable possibility' means there is evidence to suggest a causal relationship between the drug and the adverse event. Suspected adverse reaction implies a lesser degree of certainty about causality than adverse reaction, which means any adverse event caused by a drug.

A 'Serious AE (SAE) refers to any of the following cases.

- 1) Results in death, Is Life-threatening: This means that the subject was at risk of dying at the time of the event and does not mean an event based on the assumption that death could have resulted if the symptoms were more severe.
- 2) Requires inpatient hospitalization or prolongation of existing hospitalization
- 3) Results in persistent or significant disability/incapacity
- 4) Is a Congenital anomaly/birth defect
- 5) Is other important medical event that may require intervention to prevent items # 1 through #4, or may expose the subjects to danger, even though the event is not immediately life-threatening or fatal or does not result in hospitalization.

Although, important medical events that do not result in death, are not life-threatening, or do not require hospitalization, may be considered as SAEs when, based on appropriate medical judgement, they may jeopardize the subject and may require medical or surgical intervention to prevent one of the above listed results.

Examples of such medical events include allergic bronchoconstriction requiring intensive treatment in an emergency room or clinic room, blood diseases or seizures not causing hospitalization, and the occurrence of drug dependence or drug abuse.

Serious AEs and severe AEs should be distinguished. Severity is a measure of intensity, while seriousness is defined by the above criteria. For example, if the subject has mild gastrointestinal bleeding and needs overnight hospitalization for monitoring, it may be considered as a serious AE, but it is not necessarily severe. Likewise, severe AEs in terms of intensity are not necessarily serious AEs. For example, alopecia can be assessed as severe by intensity, but it is not considered a serious AE. Medical decisions and scientific judgments must be made when determining whether the AEs are serious and whether the AEs should be reported rapidly.

Adverse Event of Special Interest (AESI) are selected, non-serious adverse events. They will be reported to the sponsor within the same timeline of SAE, using a SAE report form.

The AESI in this study are as follows.

- Necrolytic migratory erythema
- Cholelithiasis

'Unexpected AE' refers to an AE pattern or risk outside of the investigator brochure (IB) or product information insert etc., that contains available relevant drug information.

'Treatment emergent adverse event (TEAE)' refers to any clinically significant event not present before exposure to study drug administration, or any event already present prior to study drug administration, that worsens in either intensity or frequency after exposure to the study drug.

The collection of AEs should continue through to the end of follow-up.

10.4.3. Recording of AE

AEs of each subject should be collected and recorded from the date of signing the ICF until the end of study participation (it refers to when the subject either discontinues or completes the study). AEs can be reported spontaneously by subject, as well as study staff can discover them from open and non-leading questions (like 'How did you feel about your health conditions since I last asked you these questions?') in the physical examination. All AEs and rescue actions should be recorded. The AE characteristics, start date (together with the time known), end date (together with time known), severity and action taken should be recorded with the seriousness of AE and causality with IP together with assessment of investigator or subinvestigator.

All AEs should be recorded using the language presented to the investigator (verbatim) individually. But this is not the case if the AE is already known as part of conditions, disease, or syndrome according to the opinion of the investigator. In the latter case, the name of condition or disease or syndrome should be specified rather than each individual symptom. The AE would be coded using MedDRA (Medical Dictionary for Regulatory Activities).

10.4.4. Severity of AE

The investigator assesses the intensity of all AEs in terms of severity in accordance with the following standard grade assessment criteria.

- 1) Mild: It is usually a temporary symptom, not affect the performance of routine daily activities of the subject. Usually, no treatment is required.
- 2) Moderate: Due to noticeable symptom, the subject feels uncomfortable. It might somewhat affect the

performance of the routine daily activities of the subject. Treatment may be required.

3) Severe: The symptoms induce considerable discomfort. It much affects the performance of the routine daily activities of the subject. It may be impossible to continue participating in the study and treatment may be required.

10.4.5. Causality with IP

The investigator will judge the causality between the AE and IP according to reviewing in many ways (e.g., past medical history, health conditions, administration time, administration status etc.) following below.

1) Related

- (1) There is an evidence that the drug has been administered.
- (2) Event or laboratory test abnormality, with plausible time relationship to drug intake.
- (3) The AE is most likely explained by the administration of this drug than any other reason.
- (4) The AE disappears with dechallenge of IP.
- (5) Rechallenge (if available) results are positive.
- (6) The AE is consistent with information already known for this drug or for the same class of drug.
- (7) The administration of this drug is judged to be due to an AE at the same level as other possible causes.
- (8) If more data are needed or an additional material is being reviewed for proper assessment of the relevance of this drug to AEs.
- (9) If the information on the causality between the administration of this drug and the AE is insufficient or cannot be determined as a conflict, and cannot be supplemented or confirmed.

2) Not related

- (1) The subject has not been administered the drug
- (2) Event or laboratory test abnormality, with unreasonable time relationship to drug intake
- (3) There is another obvious cause for AE (e.g., other drug use, latent disease and etc.) and a reasonable explanation for the AE is available.

10.4.6. Seriousness

Severity is a measure of intensity, while seriousness is defined by specified in section 10.4.2.

10.4.7. SAEs and AESI Reporting

Details of reporting SAEs and AESIs should be referenced in the Safety Management Plan (SMP). The investigator should report to the sponsor or qualified vendor writing a SAE report via fax or e-mail within 24 hours of recognizing all SAEs and AESIs regardless of their causality with the IP that occurred during the study period (the period from the subject's hospitalization to follow up visit).

SAEs and AESIs occurring after a follow-up visit (end of the study) should be reported to the sponsor by the investigator if the investigator determines that there is a reasonable causality with the IP.

The minimum information required for the initial report as follows.

- Report sender (name and contactable No. of investigator)
- Subject's identification (the screening/randomization No., not name of the subject)
- Protocol No.
- Information of SAE (start/end date, seriousness)
- Details of IP (IP dose, frequency, the first administration date, the last administration date)
- Assessment of causality

However, if available, the initial SAE report should include all of the available information about the SAE, and the written SAE report should be sent to sponsor via fax or e-mail.

Upon receipt of the initial SAE report, the sponsor's PV department reviews the information and if necessary, contacts to the investigator to obtain additional information for the assessment of the events. Details around SAE report preparation by Sponsor's PV department and timeline for submission to [REDACTED] for review and handling will be described in the SMP.

The investigator should report to the sponsor or qualified vendor a follow up report written within 24 hours of when conditions of the SAE or AESI have changed (i.e., discharge of post hospitalization, exacerbation of conditions) or additional information obtained. Details around SAE report preparation by Sponsor's PV department and timelines for submission to Medical Monitor and sponsor will be described in the SMP.

The investigator is responsible for notifying the IRB about the SAE, and the sponsor or qualified vendor is responsible for reporting the SAE to regulatory authorities in accordance with local requirements.

All serious and unexpected suspected adverse event reporting will adhere to 21 CFR 312.32 for IND drugs and 21 CFR 314.80 for marketed drugs (15-day alerts). The Institutional Review Board (IRB) and all Investigators will be notified of the alert reports per FDA regulations.

10.4.8. Follow-up of AE

AEs experienced by the subject will be monitored regardless of their causality with the IP until the resolution of the AE, or all abnormal laboratory results are returned to baseline level, or stabilization to the level allowed by the investigator and responsible medical professional, or a satisfactory description of the observed change is made, or until follow up of the subject fails

10.4.9. SUSAR (Suspected unexpected serious adverse reaction)

The sponsor should report any SUSAR to the investigator and FDA until the deadline, according to the following categories. The investigator should report to the IRB until the deadline, according to the regulation of the IRB.

- Results in death or Life-threatening: The sponsor must notify FDA of any unexpected fatal or life-threatening suspected adverse reaction as soon as possible but in no case later than 7 calendar days after the sponsor's initial receipt of the information. Other SUSARs: The sponsor must notify FDA of any other SUSAR as soon as possible but in no case later than 15 calendar days after the sponsor's initial receipt of the information.

10.5. Pregnancy

The investigator is responsible for reporting all pregnancy events occurring during the study period (from the signing the ICF until the follow up visits) to the sponsor and following up.

Pregnancy only is not considered to be an AE, unless it is suspected that the IP may have interfered with the effectiveness of the contraceptives. The choice of abortion should not be considered an AE unless it is purposed as treatment. The hospitalization for normal delivery of healthy newborn infants should not be considered a SAE. If a female subject receiving the IP becomes pregnant, the investigator should submit to sponsor the Clinical Trial Pregnancy Report within 24 hours after recognizing subject's pregnancy. Even if the subject's study participation is withdrawn or the study is terminated, the investigator should follow up the pregnancy process and results, and record.

The investigator should submit to sponsor the Clinical Trial Pregnancy Report within 24 hours after recognizing the pregnancy results (i.e., normal delivery or choice of abortion etc.).

If a female partner of a male subject receiving the IP becomes pregnant, the investigator will notify the sponsor of that pregnancy event within 24 hours of recognizing via fax or e-mail.

The investigator should acquire the ICF to share the pregnancy information, and submit to sponsor a 'clinical trial pregnancy report' within 24 hours, and follow up and notify to sponsor about the process and results of pregnancy.

All related SAEs (e.g., serious complication of maternity, abortion purposed to treatment, ectopic pregnancy, stillbirth, congenital deformation, birth defect) occurred during the pregnancy should be recorded in template of SAE report, and should be reported to sponsor or qualified vendor within 24 hours following the SAE reporting process.

10.6. Safety Reporting to Institutional Review Boards (IRBs) or Independent Ethic Committees (IECs), and Regulatory Authorities

The Sponsor or designated qualified vendor will be responsible for reporting all suspected unexpected serious adverse reactions (SUSARs) and any other applicable SAEs to regulatory authorities, Investigators, and IRBs or IECs, as applicable, in accordance with national regulations in the countries where the study is conducted.

Relative to the first awareness of the event by/or further provision to the Sponsor or Sponsor's designee, SUSARs will be submitted within 7 days for fatal and life-threatening events and 15 days for other SUSARs, unless otherwise required by national regulations.

The Sponsor or designated qualified vendor will also prepare an expedited report for other safety issues where these might materially alter the current benefit-risk assessment of an investigational product or that would be sufficient to consider changes in the investigational product administration or in the overall conduct of the study. The investigational site will forward a copy of all expedited reports to his or her IRB or IEC in accordance with national regulations.

Reporting responsibilities of Investigator under 21 CFR 312.64(b) and Sponsor under 21 CFR 312.32(c)(1)(i) for serious and unexpected suspected adverse reactions will be followed.

11. Statistical analysis and statistical consideration

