		Week 10	Day 78	Pre-dose 12th dosing
				8 h after 12th dosing
			Day 79	24 h after 12th dosing
			Day 80	48 h after 12th dosing
			Day 81	72 h after 12th dosing
	F/U	OPD	Day 82	96 h after 12th dosing
			Week 13	168 h after 12th dosing
			Week 15	504 h after 12th dosing
			Week 17	840 h after 12th dosing

[PK SAMPLING SCHEDULE] PARTs 1 and 2 - COVID-19 Modification

PK sampling schedule					Time window	Added Time window
Treatment period	OPD	Week 1	Day 1	Pre-dose 1st dosing	-60 min	
				4 h after 1st dosing	±10 min	
			Day 3	48 h after 1st dosing	±30 min	±1 day
			Day 5	96 h after 1st dosing	±30 min	±1 day
		Week 2	Day 8	Pre-dose 2nd dosing	-60 min	
		Week 2	Day 10	48 h after 2nd dosing	±30 min	±1 day
			Day 11	72 h after 2nd dosing	±30 min	±2 days
		Week 3	Day 15	Pre-dose 3rd dosing	-60 min	
			Day 17	48 h after 3rd dosing	±30 min	±1 day
			Day 18	72 h after 3rd dosing	±30 min	±2 days
		Week 4	Day 22	Pre-dose 4th dosing	-60 min	
		Week 5	Day 29	Pre-dose 5th dosing	-60 min	
		Week 6	Day 36	Pre-dose 6th dosing	-60 min	
		Week 7	Day 43	Pre-dose 7th dosing	-60 min	
		Week 8	Day 50	Pre-dose 8th dosing	-60 min	
		Week 9	Day 57	Pre-dose 9th dosing	-60 min	
		Week 10	Day 64	Pre-dose 10th dosing	-60 min	
		Week 11	Day 71	Pre-dose 11th dosing	-60 min	
		Week 12	Day 78	Pre-dose 12th dosing	-60 min	
				4 h after 12th dosing	±10 min	
			Day 80	48 h after 12th dosing	±30 min	±1 day
			Day 82	96 h after 12th dosing	±30 min	±1 day
F/U	OPD	Week 13	Day 85	168 h after 12th dosing	±2 days	
		Week 15	Day 99	504 h after 12th dosing	±2 days	
		Week 17	Day 113	840 h after 12th dosing	±2 days	

[ABBREVIATIONS AND DEFINITIONS]

ABP	Ambulatory blood pressure
ADA	Anti-drug antibody
AE	Adverse event
AESI	Adverse Event of Special Interest
ALP	Alkaline phosphatase
ALT	Alanine aminotransferase
anti-PEG	Anti-polyethylene glycol
AST	Aspartate aminotransferase
AUC	Area under the concentration-time curve
AUC _{%extrap}	Percentage of AUC _{inf} that is due to extrapolation beyond t _{last}
AUC _{0-t}	Area under the concentration-time curve from predose (time 0) to the time of the last quantifiable concentration
AUC _{inf}	Area under the concentration-time curve from predose (time 0) extrapolated to infinite time (AUC _{0-t} + C _{last} /λ ₂)
BMI	Body mass index
BP	Blood pressure
bpm	Beats per minute
BUN	Blood urea nitrogen
CFR	Code of Federal Regulations
CHI	Congenital hyperinsulinism
Cl	Chloride
CL/F	Total body clearance
C _{max}	Maximum concentration
CO ₂	Carbon Dioxide

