5.2. Inclusion Criteria

Subjects who meet all of the following criteria are considered eligible for participation in the study.

- 1) Male or Female subjects
- 2) Age ≥ 18 to ≤ 65 years at Screening visit.
- 3) Body Mass Index (BMI) $\geq 30 \text{ kg/m}^2$ or $27 \text{ kg/m}^2 \geq$ with presence of comorbidities (Subjects in Part 1: dyslipidemia and or hypertension except for Type 2 (T2) DM, T2DM subjects in Part 2: dyslipidemia and/or hypertension with T2DM) with/without medication treatment and have had stable weight for 3 months (weight changes less than 5%), Untreated dyslipidemia is defined as LDL $\geq 160 \text{ mg/dL}$, or Triglyceride $\geq 150 \text{ mg/dL}$, or HDL $< 40 \text{ mg/dL}$ for male and $< 50 \text{ mg/dL}$ for female, untreated hypertension is defined as Systolic Blood Pressure ≥ 140 or Diastolic Blood Pressure $\geq 90 \text{ mmHg}$. -
- 4) The criteria for HbA1c and FPG (Fasting Plasma Glucose) are as below.
 - ① Subjects in Part 1: 'FPG $< 5.6 \text{ mmol/L}$ (100 mg/dL)' and 'HbA1c $< 5.7\%$ ' (But, if the result is out of the reference range at the screening visit, it can be tested again on another day by laboratory analysis.)
 - ② Subjects in Part 2 with DM: the subjects diagnosed as type 2 DM, and stably treated with HbA1c $\leq 9\%$ for 3 months by Metformin only.
- 5) Female subjects must be non-pregnant and non-lactating. Females of childbearing potential must use highly effective contraceptive methods, stable at least 2 months prior to the screening. Male subjects should be surgically sterile (at least 1 year after vasectomy) or sterilized from the screening visit to 60 days after administration of IP, or if the male subject has a sexual relationship with a female partner of childbearing potential, the male subject is required, and the female partner should be encouraged to use a valid contraceptive method (e.g., condom, spermicidal form/gel/ film/cream suppository combination, etc.) during the study period.
- 6) Subjects who agree to participate this study voluntarily and to give written informed consent.

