- ① In-house 1: The IP will be administered on Day 1, and blood sample collection will be conducted during the hospitalization assessment period (until Day 8) for the safety monitoring and PK and PD assessment.
- ② In-house 2: The subject will return on Day 77 and after admission, the IP will be administered on Day 78, and blood sample collection will be conducted during the hospitalization assessment period (until the Day 82) for the safety monitoring and PK and PD assessment

Per COVID-19 modification, the treatment period is performed over 12 weeks, including baseline and outpatient visits.

5) OPD visits

The OPD visits will be conducted on Day 10, 11, 15, 17, 18, 22, 29, 36, 43, 50, 57, 64, 71 with safety and PK/PD assessments.

Per COVID-19 modification, all visits may be performed as outpatient visits.

6) Follow up

The follow up visit will be conducted on Day 85, 99, 113 with safety and PK/PD assessments.

7) End of treatment (EOT) visit

Subjects who withdraw their consent or withdraw from participation in the study may have an EOT visit as soon as possible. The EOT may be performed after withdrawal of the subject's consent or withdraw from participation in the study as soon as possible. The planned evaluation and procedures for the follow-up visit on Day 113 may be conducted at the EOT. Specific assessments from the other follow-up visits may be added per request, if needed.

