To ensure that female partners of male subjects exposed to clinical trial medications will not get pregnant, or to prevent any partner from being exposed to the semen of the male subject, a male subject who is not surgically sterile, (defined as at least 1 year after vasectomy), must use an acceptable method of contraception from screening visit until 60 days after IP administration. If the subject would prefer abstinence, Sexual abstinence must be consistent with a routine lifestyle of sexual inactivity. Periodic abstinence [e.g., calendar day, ovulation, symptom-related method or post ovulation method] and coitus interruptus is not an acceptable method of contraception). Condoms should be used with spermicidal foam/gel/film/cream/ suppository. Contraceptive methods for female partners should also be encouraged and are the same as those stated in the section below for female subjects of child-bearing potential. The contraceptive method must be used for a period of 60 days after administration of the IP. The adequacy of other contraceptive methods is assessed by the investigator on a case-by-case basis. Male subjects with a pregnant female partner at signing of informed consent, may be included in the study, as semen of male subject that will be exposed to trial medication cannot lead to conception.

Females must be non-pregnant and non-lactating, and either surgically sterile (eg, bilateral tubal occlusion, hysterectomy, bilateral salpingectomy, bilateral ovariectomy) or postmenopausal for >12 months. If females' sterility or postmenopausal status is confirmed, no pregnancy testing is required during the study. The site will make an effort to retrieve medical records to document the sterility, however, the absence of records will not exclude the subject. In case that medical records cannot be obtained, serum pregnancy testing will be conducted at Screening, and urine pregnancy testing will be conducted throughout the study. Postmenopausal status will be confirmed through testing of FSH

levels outside the normal range (as specified by responsible lab) at screening for amenorrheic female subjects < 60 years of age.

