Female subjects who state they are postmenopausal at the screening visit but have an FSH value that does not correspond with a postmenopausal FSH level, may have a serum hCG pregnancy test performed on a separate day. If screening sample is within stability range, the serum hCG pregnancy test may be performed out of the same sample. If test is negative and the subject agrees to be on a highly effective contraceptive method, subject may be enrolled in the study at the discretion of the Investigator.

Female subjects of childbearing potential do not need to have a serum hCG test at Screening, as urine hCG test will be assessed at Screening. Female subjects of child-bearing potential must use highly effective contraceptive methods. Highly effective contraceptive methods are considered those with failure rate less than 1% undesired pregnancies per year with perfect use, including hormonal intrauterine devices (coil), oral hormonal contraceptives, sexual abstinence, or a surgically sterilized partner. If the subject would prefer abstinence, sexual abstinence must be consistent with a routine lifestyle of sexual inactivity. Periodic abstinence [e.g., calendar day, ovulation, symptom-related method or post ovulation method] and coitus interruptus is not an acceptable method of contraception). Oral hormonal contraceptives have to be taken at least 2 months prior to Screening until 30 days after the last Follow-up Visit. The adequacy of other contraceptive methods is assessed by the investigator on a case-by-case basis.

During the course of the study, regular serum human chorionic gonadotropin (hCG) pregnancy tests will be performed for sterilized women, when medical records are not available. In addition to a negative serum hCG pregnancy test at Screening, subjects also must have a negative urine hCG pregnancy test at check-in to in-house periods.

3) Alcohol and Caffeine

Alcohol consumption should be avoided within 48 hours prior to any visit and during the subject's stay in the institution. The subjects should not consume more than 3 units of alcohol per days during the study period (1 unit is same as about a cup of beer [284 mL], a small cup of wine [125 mL], one standard volume of spirits [25 mL], a cup of raw rice wine (Makgeolli)[250 mL]).

Caffeinated food or beverages (e.g., chocolate, coffee, tea, cola, Red Bull) are not allowed within 24 hours prior to each visit and during the subject's stay in the institution.

4) Smoking and cigarettes

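### Male contraception ends about 25 days earlier in section 5.2 than in 10.2.3, and the 10.5 pregnancy-reporting duty stops before the contraception periods in 10.2.3 do

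*Protocol*

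**What the plan says.** All of this is in the protocol.

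- **Schedule (10.1.1).** At the second in-house stay "the IP will be administered on Day 78"; this is the twelfth and last dose. "The follow up visit will be conducted on Day 85, 99, 113 with safety and PK/PD assessments". The PK sampling schedule places the last visit "840 h after 12th dosing".
- **Men, section 5.2 item 5, repeated in the synopsis.** If the partner could conceive, "the male subject is required, and the female partner should be encouraged to use a valid contraceptive method". The sentence then limits this to the duration of the study. The same item mentions 60 days after dosing, but only for men who are sterilised.
- **Men, section 10.2.3, Contraception.** A man who is not surgically sterile "must use an acceptable method of contraception from screening visit until 60 days after IP administration". Later in the paragraph: "The contraceptive method must be used for a period of 60 days after administration of the IP".
- **Women, section 10.2.3.** "Oral hormonal contraceptives have to be taken at least 2 months prior to Screening until 30 days after the last Follow-up Visit". No end date is given for the other accepted female methods.
- **Reporting, section 10.5.** The investigator is responsible for "reporting all pregnancy events occurring during the study period (from the signing the ICF until the follow up visits"). Reports are due within 24 hours of recognition, for female subjects and for partners of male subjects. A pregnancy under way is followed to its outcome even after withdrawal or the end of the study.

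**The concern.** Two things do not fit together.

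First, sections 5.2 and 10.2.3 set different end points for the same men and the same precaution. A site working from the inclusion criterion would tell a man he may stop at the end of the study. A site working from the restrictions section would tell him to continue. The text does not say which one governs.

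Second, the sponsor chose contraception periods that outlast the final visit, yet the duty to report pregnancies ends at that visit. A pregnancy beginning in between falls inside the protocol's own precaution period and outside its reporting duty. Safety is a primary objective, and such a pregnancy could be absent from the safety record although every instruction was followed.

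**Working it through.** No statistical calculation applies; this is calendar arithmetic plus a comparison of passages.

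**Reproducing the plan's own date.** Last dose Day 78, last visit 840 h later: 78 + 840/24 = 78 + 35 = Day 113. The same rule gives Day 85 (78 + 168/24) and Day 99 (78 + 504/24), both as scheduled.

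**Where the study ends.** Section 10.5 closes the study period at the follow-up visits. Section 10.4.7 also runs it to the follow-up visit and treats that visit as the end of the study. Section 10.2.3, under Others, bars sperm donation for the whole study and, in addition, for 60 days after dosing, so the protocol itself treats these as two separate periods. On this reading the 5.2 requirement for men using a contraceptive method ends at Day 113.

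**Men under 10.2.3.** Counting from the last dose: 78 + 60 = Day 138. Difference from 5.2: 138 − 113 = 25 days. With the ±2-day window on the Day 113 visit the difference is 138 − 115 = 23 to 138 − 111 = 27 days. Counting from the first dose would give 1 + 60 = Day 61, before treatment ends, so the last dose is the sensible reading, but the text does not state it.

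**Women on oral hormonal contraceptives under 10.2.3.** 113 + 30 = Day 143, or Day 141 to Day 145 with the visit window. The interval after the last visit is 30 days in every case. For other female methods no date can be computed.

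**Side by side**

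| Item | Source | End | Days past Day 113 |
|---|---|---|---|
| Pregnancy reporting (onset) | 10.5 | Day 113 | 0 |
| Men using a contraceptive method | 5.2, synopsis | Day 113 | 0 |
| Non-sterile men | 10.2.3 | Day 138 (from last dose) | 25 |
| Women, oral hormonal | 10.2.3 | about Day 143 | 30 |
| Women, other methods | 10.2.3 | not stated | – |

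**Does another clause cover the interval?** Section 10.4.7 requires reports after the follow-up visit only for serious events and events of special interest that the investigator considers causally related. Section 10.5 says pregnancy alone is not an adverse event unless the product is suspected of having impaired the contraceptive. An uncomplicated pregnancy beginning on, say, Day 120 is therefore caught by neither. The 24-hour rules set how fast to report, and the rule on following pregnancies after study end concerns outcome; neither moves the limit on onset set by the first sentence of 10.5.

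**The case against.** The case for leaving the text alone has real substance.

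- **Late recognition.** A reader might infer that a conception shortly before Day 113, noticed afterwards, goes unreported. The documents do not support that. Section 10.5 turns on when the pregnancy occurs, and its clock starts at recognition, so these pregnancies are already reportable.
- **Three end dates for one window.** A reader might also see a single window given three different ends. Male contraception, female oral contraception and pregnancy reporting are separate items and may legitimately differ. The only direct contradiction is 5.2 against 10.2.3 for men.
- **All women to Day 143.** That date is stated for oral hormonal methods only. Section 5.2 sets no end date for women, so it does not conflict with 10.2.3 for them.
- **Exposure.** It is tempting to call any pregnancy after Day 113 an exposed one. The protocol does not describe the contraception periods as exposure windows. Thirty-five days is five half-lives for any half-life up to 840/5 = 168 h; the animal values in section 3.4 are 26.6 to 56.2 h, and no human value is given.
- **Existing safeguards.** There is a urine pregnancy test on Day 113, and a congenital anomaly counts as a serious adverse event under 10.4.2.
- **Precedence.** Section 10.2.3 is the more detailed section and uses mandatory language, so a careful site would probably follow it.

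The first four limit how far the point reaches. The last two reduce the practical risk without removing the problem: the Day 113 test cannot detect a pregnancy that begins later, no partner testing or contact is scheduled after Day 113, and the protocol has no rule that 10.2.3 prevails over 5.2.

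**Conclusion.** The point holds, as a matter of reconciling passages.

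1. Section 5.2 item 5 and the synopsis contradict 10.2.3 for non-sterile men using a contraceptive method, by about 25 days (23 to 27 with the visit window). This assumes that the 60 days run from the last dose, that the last dose falls on Day 78, and that the study period ends as 10.5 describes.
2. The onset limit in 10.5 falls short of the contraception periods in 10.2.3 by the same 25 days for men, and by 30 days for women on oral hormonal contraceptives. In that interval only a pregnancy leading to a serious event judged related to the product has to be reported.

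It does not follow that pregnancies are being lost, that those after Day 113 involve drug exposure, or that any one contraception period is the right one. No endpoint, analysis or dose-escalation decision is affected. It merits correction because a site could follow the text exactly and still miss a precaution or a report that the sponsor evidently wanted.

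**What to change.** The sponsor should:

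- reconcile the synopsis and section 5.2 item 5 with section 10.2.3, so that men using a contraceptive method are given one end point;
- state in 10.2.3 which dose the 60 days are counted from;
- align the reporting period in 10.5 with whichever contraception periods are kept, and say whether an end date is intended for female methods other than oral hormonal ones.

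Which periods to keep is a clinical decision for the sponsor, and none is proposed here. The cost is protocol wording, plus a report when the site learns of a pregnancy. No visit, sample or analysis is added.
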